1.0 BACKGROUND INFORMATION AND RATIONALE

○ Introduction

Physical therapy patients experiencing musculoskeletal pain often lack effort and consistency when performing aquatic exercises. Studies have shown that the use of acoustic stimuli, such as music and the beeps of a metronome, improve performance and efficiency in runners. However, it has not been determined if the use of a metronome can improve the outcomes of patients participating in aquatic physical therapy.

○ Relevant Literature and Data

In 2012, one of two adults in the United States were diagnosed with musculoskeletal conditions. In the same year, 25.5 million people lost an average of 11.4 days of work due to back and neck pain. (1)

The benefits of aquatic therapy make it well suited for the treatment of musculoskeletal conditions. These benefits include decreased weight bearing, the thermal and compressive effects of water on the body, and less cardiovascular stress during exercise. (2)

In a 2008 study it was demonstrated that the use of acoustic pacing device can improve consistency and performance during and between exercise sessions in an aquatic environment among runners(3) Studies have also shown that an aquatic exercise program can improve strength and function among varied age groups.(4,5) However, what isn't known is if the use of an acoustic pacing device, such as a metronome, can improve the outcomes of patients in an aquatic therapy program.

STUDY OBJECTIVES

○ Primary Objective

To determine if the use of a metronome improves measures of functional outcome in aquatic therapy.

2.0 INVESTIGATION PLAN

○ General Schema of Study Design

Quasi-experimental

- Study Duration, Enrollment and Number of Sites
 - 2.○ .1 Date Range of Study
(January 3, 2019 - December 1st, 2019)
 - 2.○ .2 Total Number of Study Sites
Aultman Tusc Therapy
 - 2.○ .3 Total Number of Subjects Projected 120
The statistician projected the study would require 102 participants. I will recruit up to 120 to allow for unforeseen issues. The 120 participants will be divided into a control group of approximately 60 and the metronome group of approximately 60.
- Study Population
 - 2.○ .1 Inclusion/Exclusion Criteria
All patients over the age of 18 will be included in the study except for those that have identified themselves as being pregnant on intake, and those that are unable to hear the metronome or unable to hear it when their hearing aide is removed during treatment.

STUDY PROCEDURES

○ Procedures Involved

During their initial evaluations and again at re-evaluation or discharge, patients will be assessed using a 30 second sit to stand. The patient will be asked to rate their progress using the global rating of change scale at re-evaluation or discharge. The patients will be asked to rate their pain using a numerical pain scale. Their reported pain level will be recorded before and after each treatment. The number reported on initial evaluation and at discharge will be used in the study. The above numbers will be recorded in the patient's electronic chart and on the de-identified flow sheet. All patients will be educated on proper performance of aquatic exercises following normal physical therapy procedures. The patients will be randomly placed into two groups: a control group and a group exercising with the pacing of a metronome. (The metronome does not appear in the FDA's product classification database as a medical device.) The patient's will be randomized by placing 20 poker chips in a bag. There will be 10 white pieces with the letter C and 10 red pieces with the letter M. When a patient is chosen for the study a piece of paper will be drawn out of the bag and they will be assigned to a group by the letter chosen. The bag will be refilled and the process repeated until the study groups are filled.

The two groups will follow exercise protocols based on their diagnosis. Each session will last approximately 30 to 45 minutes. The length of each treatment will be recorded on the flow sheet. The BORG scale (a valid, subjective measure of perceived exertion) will be used as a monitoring device to ensure that a desired level of exercise intensity is reached. The desired level is a score between 12 and 16. The patients will be asked to rate their level of exertion at the end of each session. Intensity of the exercises will be adjusted the next session if the patient's reported level of exertion does not fall within the desired range. The pain rating, noted above, and the BORG number will be recorded for both groups in the chart and flow

sheet as will be the metronome beats per minute for the study group. The beats per minute of the metronome will be adjusted to the patient's pain free exertion level. Patients in both groups will start with 10-20 repetitions of the exercises depending on their physical ability. The repetitions will be progressed as the patient's strength and endurance improve and noted in the chart and the flow sheet.

The patients in the metronome group will have the metronome synchronized as previously noted on their second aquatic therapy treatment. The beats per minute (BPM) will be increased on the metronome during the series of treatments until the patient can no longer maintain proper technique with the exercises. The patient will be cued to keep pace with the beat of the metronome during the duration of the exercise.

- Visit Schedule
Each individual will participate in the study for the duration of their physical therapy plan of care, typically 10 to 12 visits. Enrollment will be on going during the study period in order to recruit the needed number of participants. Estimated completion date will be May 1st, 2019.
- Recruitment Procedures
Participants will be recruited during their initial physical therapy evaluations. The study will be explained to them and the consent forms will be signed during their first aquatic therapy treatment.
- Data Collection and Management
 - 2.○ .1 Data sources
Participant's initial evaluation will be used to determine age, gender and diagnosis.
 - 2.○ .2 Data Elements to be Abstracted
 - *Numerical pain scale rating*
 - *30 second sit to stand*
 - *BORG (perceived rating of exertion)*
 - *Global Rating of Change (GRoC)*

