5.0 STATISTICAL CONSIDERATIONS

- Primary and Secondary Endpoints
To determine if the use of a metronome increases intensity of exercise performance as measured by an increase in the BORG scale.
To determine if the use of a metronome improves self-reported and objective measures of functional outcome performance by using the GROC and the 30 second sit to stand and noting an improvement in scores.
- Measures to Avoid Bias

Study participants will be randomized as previously noted.

Statistical Methods, Sample Size and Power

A minimum of 102 participants will be needed for a medium effect, a power of 0.8 and a level of significance of 0.05. The data analysis plan will be an Analysis of Covariance (ANCOVA), with the baseline data as the covariate.

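### Borg exertion is held to 12–16 in both groups during treatment and is also an endpoint, so the plan biases its own Borg comparison toward zero

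*Protocol*

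**What the plan says.** In Protocol section 2.0, under Study Procedures, the Borg scale "will be used as a monitoring device to ensure that a desired level of exercise intensity is reached". The target is explicit: "The desired level is a score between 12 and 16". Patients rate exertion at the end of every session, and an out-of-range score has a consequence: "Intensity of the exercises will be adjusted the next session if the patient's reported level of exertion does not fall within the desired range". The paragraph opens by addressing both groups, and nothing limits the rule to one of them. The size of the adjustment is not given.

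Metronome tempo has its own instructions. "The beats per minute of the metronome will be adjusted to the patient's pain free exertion level", and the tempo "will be increased on the metronome during the series of treatments until the patient can no longer maintain proper technique". Neither sentence mentions a Borg value.

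Section 5.0 lists as its first endpoint: "To determine if the use of a metronome increases intensity of exercise performance as measured by an increase in the BORG scale". No endpoint is labelled primary. The primary objective, stated after section 1.0's background, is functional: "To determine if the use of a metronome improves measures of functional outcome in aquatic therapy". For analysis, "The data analysis plan will be an Analysis of Covariance (ANCOVA), with the baseline data as the covariate".

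**The concern.** The same score is both the quantity that treatment controls and the quantity on which the groups are compared. A metronome that makes patients work harder raises Borg, and the protocol responds to high scores by changing the next session. A control patient who does too little scores low, and the protocol responds to that as well. Both responses shrink the contrast that section 5.0 sets out to detect, even if every instruction is followed perfectly. ANCOVA on baseline cannot restore a difference that was removed during treatment.

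At stake is how the Borg result is read. A small or null difference could be reported as showing that pacing does not raise intensity, when part of the difference was taken out by the protocol's own corrections. The 30 second sit to stand and the global rating of change (GRoC) are not steered in this way.

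**Working it through.** **Direction, from the text alone.** Suppose, for illustration, that the metronome adds 2 points and each correction is 1 point.

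- Control 15, metronome 17: the metronome patient is brought to 16, and the difference goes from 2 to 1.
- Control 11, metronome 13: the control patient is brought to 12, and the difference goes from 2 to 1.
- Control 13, metronome 15: both are in range, and the difference stays at 2.

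Corrections act only outside the band and, on balance, oppose the treatment effect. The result is attenuation, not elimination.

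**The plan's own figure.** Section 5.0 gives 102 participants for a medium effect (taken as d = 0.5), power 0.8 and alpha 0.05. A one-sided two-sample t-test gives 51 per group, 102 in total. A two-sided t-test gives 128. A two-sided ANCOVA gives 102 if the baseline correlation is about 0.45. Sidedness is not stated. The present point does not depend on this; 51 per group is used below.

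**Size, by simulation.** The protocol supplies the 12–16 band, the next-session rule, 10 to 12 visits, pacing from the second treatment, and ANCOVA on baseline. Everything else is assumed:

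- Model: Borg at visit v of V = round[b + a(v) + E × (v − 1)/(V − 1) + e], kept within 6–20, with the E term in the metronome group only. Here b is the patient's own level, a(v) the accumulated corrections and e session noise. The first, unpaced visit is the covariate.
- Mean starting Borg 12, 14 or 16; between-patient SD 1.5 or 2.0; session SD 1.0.
- Correction of 1 point, 2 points, or to the nearest limit.
- E = 0.5 × √(1.5² + 1.0²) = 0.90, or 0.5 × √(2.0² + 1.0²) = 1.12 points at the last visit.
- Settings: 3 means × 2 SDs × 3 corrections × 2 visit counts = 36.
- Power: noncentral t, 99 df, two-sided 0.05, noncentrality = (ANCOVA standardised difference) × √(51/2).

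| Analysis, 36 base settings | Difference retained | Power without rule | Power with rule | Power falls in |
|---|---|---|---|---|
| Last visit | 40–68% | 0.91–0.98 | 0.27–0.84 | 36 of 36 |
| Mean of paced visits | 51–76% | 0.76–0.88 | 0.62–0.94 | 23 of 36 |

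A rerun with fresh code and a new seed agreed to within 0.03 and gave the same counts. When visits are averaged, power can rise although the difference shrinks, because the rule also narrows the spread of scores.

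**Sensitivity, last visit.**

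- Session SD 0.75: 48–75% retained. Session SD 1.5: 26–57% retained.
- Between-patient SD 1.0, session SD 0.5, mean start 13–14, 11 visits: 78–91% retained. Power goes from about 0.95 to 0.88–0.92 with 1-point corrections and to 0.70–0.78 with 2-point corrections.
- Bounding case, full effect from the second treatment: 4–38% retained. This fits the rising-tempo instruction less well than a gradual build-up.

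The difference shrank in every setting tried.

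**The case against.** Four arguments on the other side deserve weight.

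**The inputs are assumed.** Starting Borg, spreads, correction size, effect shape and analysed visit are not in the protocol. With small spreads centred in the band the loss is mild. This stands: the direction is established, the size is not. A reader might infer that the Borg endpoint is certain to be underpowered, or that the contrast is wiped out. The document supports neither. The band covers five scores, in-range differences are untouched, and with visits averaged power falls in only 23 of 36 base settings.

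**The comparison under monitored care is a legitimate question.** One may ask whether the metronome raises exertion while exertion is being kept in range. That is true, but section 5.0 words the endpoint as whether the metronome increases intensity, and a null answer to the narrower question would be read as an answer to the wider one.

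**The consequence is limited.** Borg is not labelled primary and the primary objective is functional. This stands and bounds the importance of the point.

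**The tempo rules are not in contradiction.** A reader might infer that a metronome patient at Borg 17 with good technique is under two opposing orders: raise tempo and reduce intensity. The text does not require that. The intensity rule already covers the metronome group, it can be met through repetitions or by pausing tempo progression, and the tempo sentence describes a progression over the series, not a rise at every session. What is missing is only a statement of which instruction takes priority.

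**Conclusion.** The point holds in a limited form. Following the protocol exactly biases the between-group Borg difference toward zero, because scores outside 12–16 trigger corrections in both groups; differences inside the band survive. That conclusion rests on the text. The magnitude does not: under the base and smaller assumed spreads about 40% to 90% of a gradually building difference remains at the last visit, and as little as 26% with noisier session ratings. Loss of power is likely if the last visit is analysed and uncertain if visits are averaged. The functional outcomes in the primary objective are not steered this way, so the trial remains viable. This is a worthwhile, inexpensive improvement to one endpoint and its interpretation. The tempo wording is a minor clarification.

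**What to change.** In section 5.0:

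- Remove the increase in Borg as an efficacy endpoint, and report Borg by group and session as a check on the intensity delivered.
- Rest the conclusion on the 30 second sit to stand and GRoC, which section 5.0 already names for functional outcome.
- Report beats per minute, repetitions and treatment length descriptively as delivered dose, not as replacement endpoints, since the metronome itself partly sets the repetition rate.
- State that a small or null Borg difference is not evidence that the metronome does not raise intensity.

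In section 2.0, add one clarifying sentence that the 12–16 rule also governs tempo progression, and add the three dose items to the list of data elements to be abstracted.

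Moving the Borg endpoint to the second treatment, before the rule can react to pacing, is not recommended. If the effect builds evenly, only 1/11 to 1/9 of it is present then, and power is about 0.06–0.08.

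**Cost.** A few sentences; no added patients, visits, staff or measurements, because the dose items are already on the flow sheet. The real downside is that the trial no longer tests perceived intensity as an efficacy outcome. Applying the band to tempo may hold back some patients who could go faster with good technique, and would narrow later Borg differences further, which matters less once Borg is only a check.

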3.0 STUDY ADMINISTRATION

- Data Quality. Data collection in the pool will be limited to two Physical Therapist Assistants. There will be 1- 4 Physical Therapist collecting data during the initial evaluation and re-evaluation depending on which PT is referring the patient for aquatic therapy.

Privacy and Confidentiality

- All laws ensuring privacy and confidentiality governed through HIPPA will continue to be practiced.
- Data with patient identifiers will be de-identified by me.
- All files will be stored in a secured and locked location at Aultman Tusc Therapy.

- Confidentiality
See above
- Regulatory and Ethical Considerations
 - 3.○ .1 Risk Assessment
The participants in the study will face no additional risk than those not in the study. As normal physical therapy procedures will be followed for patients receiving aquatic therapy.
 - 3.○ .2 Potential Benefits of Study Participation
Anticipated benefits of participation in the study will be a decrease in the number of visits needed to improve strength and function.
 - 3.○ .3 Informed Consent/Assent and HIPAA Authorization
Informed consent will be obtained by the primary/secondary investigators during the patient's first aquatic therapy treatment. No data will be collected until that point.
 - 3.○ .3.1 Waiver or Alteration of Consent (requesting a waiver)

N/A
 - 3.○ .3.2 Waiver of HIPAA Authorization
N/A

4.0 SAFETY MANAGEMENT

- Adverse Events Collection/Reporting
Non-invasive use of a metronome
- Data Safety Monitoring Plan
Physical therapy guidelines are already in place to ensure data safety of the patient participating in physical therapy treatment.

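### The protocol sets no rule for collecting adverse events and uses only the first and last pain scores, so harm would not be systematically captured or compared by arm

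*Protocol*

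**What the plan says.** Protocol section 4.0 has two entries. Under Adverse Events Collection/Reporting the whole text is "Non-invasive use of a metronome". Under Data Safety Monitoring Plan it is "Physical therapy guidelines are already in place to ensure data safety of the patient participating in physical therapy treatment".

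Section 3.0, Risk Assessment, states: "The participants in the study will face no additional risk than those not in the study". The reason follows: "As normal physical therapy procedures will be followed for patients receiving aquatic therapy".

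Section 2.0, Procedures Involved, makes two statements about pacing, which apply to the metronome arm only. The first is "The beats per minute of the metronome will be adjusted to the patient's pain free exertion level". The second is that the beats per minute are to be "increased on the metronome during the series of treatments until the patient can no longer maintain proper technique with the exercises". In both arms exertion is monitored against a BORG target of 12 to 16, and intensity is changed at the next session if the score falls outside it.

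On pain, section 2.0 says "Their reported pain level will be recorded before and after each treatment". It then names the initial-evaluation and discharge scores as the ones the study will use. Pain and BORG go into the chart and flow sheet for both groups. The Data Elements to be Abstracted are four: pain rating, 30-second sit to stand, BORG and Global Rating of Change.

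**The concern.** What is collected from patients is settled in the protocol. An analysis plan cannot tabulate an injury or a reason for withdrawal that nobody wrote down. Here the protocol has the right heading, but the text beneath it gives no definition of an event, no method of finding one, no form, no timeframe and no reporting line.

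This matters because the arms differ in a way that bears on tolerability. One arm is cued to keep pace with a beat that rises over the course of treatment, and section 5.0 names greater exercise intensity as something the trial hopes to show. That the device is non-invasive says nothing about the exercise it drives. If the plan is followed as written, the report could show better function in the metronome arm with no planned account of whether pain flares, interrupted sessions or symptom-driven withdrawals were more frequent there. The no-additional-risk statement would remain untested.

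**Working it through.** The protocol gives no safety figure to reproduce, so the main check sets the text side by side.

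**Step 1. What is recorded and what the plan does with it (sections 2.0, 4.0 and 5.0).**

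| Possible harm | Recorded? | Planned use |
|---|---|---|
| Pain flare within a session | Yes: before and after, both arms, flow sheet | None; only initial-evaluation and discharge scores |
| High exertion | Yes: BORG each session, both arms | Intensity adjustment; endpoint in section 5.0 |
| Injury or other event in the pool | No item | None |
| Session stopped early | Session length only; no item for stopping or its reason | None |
| Withdrawal | Number follows from allocated minus completed; no item for the reason | None |

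The gap is therefore of two kinds. Some harms have no recording item. Pain flares are recorded, but the readings are not put to use.

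**Step 2. Scale of the unused pain data.** Inputs from section 2.0: typically 10 to 12 visits, two readings per session, up to 120 patients, about 60 per arm, metronome introduced at the second aquatic treatment. Assumptions: every visit is an aquatic session and nobody drops out.

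- Session readings per patient: 2 × 10 = 20 to 2 × 12 = 24.
- Values used per patient: 2. As a rough ratio, 2/20 = 10% to 2/24 = 8.3%. It is rough because the initial-evaluation score need not be one of the pool readings.
- Before/after pairs, both arms: 120 × 10 = 1,200 to 120 × 12 = 1,440.
- Pairs in the metronome arm while paced: 60 × (10 − 1) = 540 to 60 × (12 − 1) = 660.

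**Step 3. What event collection could show.** This gives scale and does not measure the defect. The per-arm size is 51 (half of the stated minimum of 102) to 60. The event rates are assumptions.

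- One-sided 95% upper limit with zero events, 1 − 0.05^(1/n): 5.7% at n = 51 and 4.9% at n = 60.
- Chance of at least one event, 1 − (1 − p)^n: 0.64 to 0.70 at p = 2%, and 0.93 to 0.95 at p = 5%.
- Power to separate 5% from 15% between arms: 0.39 to 0.45.

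A by-arm safety table would be descriptive. It could show a common problem but could not exclude an uncommon one.

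**Step 4. Statements that do not fit together.** Section 3.0 bases unchanged risk on normal procedures. Section 2.0 gives one arm a step that the other does not have. Within section 2.0, one statement ties pacing to pain-free exertion and another lets it rise to the point where technique is lost. The text does not say how these two limits relate, and section 3.0 addresses neither.

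**The case against.** The strongest reply is that the protocol does look after and observe its patients. Pacing is tied to pain-free exertion, BORG is monitored in both arms with adjustment at the next session, and section 4.0 relies on existing physical therapy guidelines. Pain and BORG are on the flow sheet for both groups, and a by-arm safety table is commonly left to an analysis plan, which is not shown here.

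Much of this stands, and it rules out several stronger readings. A reader might infer that harm in the metronome arm could not be detected, that there would be no data on it, or that the session pain scores are thrown away. The documents do not support this: the scores are kept for both arms, a comparison could be made from them, and withdrawals could be counted. A reader might also infer that patients are exercised to failure. The sentence on technique can equally be read as the point at which increases end over a series of treatments, and it stands beside the pain-free limit.

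The reply does not supply a recording rule. Adjusting a session manages the patient but records no event. The guidelines are cited without any study item or comparison by arm. On pain, the protocol itself names the two scores the study uses, so an analysis plan that used the rest would have to go beyond it.

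**Conclusion.** The point holds in a limited form. The protocol has no adverse-event collection rule and no item for events or for reasons for withdrawal, and it puts only two pain values per patient to use out of the roughly 20 to 24 session readings taken alongside them. Harm would not be systematically captured or compared by arm. The counts assume 10 to 12 visits, all of them aquatic, with full follow-up.

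It would go too far to conclude that the metronome arm is unsafe or that the no-additional-risk statement is false. The documents show only that this statement and the two pacing statements have not been brought into agreement, and this review takes no position on which should govern. The upper limits of 4.9% to 5.7% describe what a completed collection with no events could say; they do not size the defect. The primary analysis, sample size and efficacy estimates are untouched. It is an improvement that should be made, mainly because it costs so little.

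**What to change.** 1. Replace the adverse-event entry in section 4.0 with a rule to record on the existing flow sheet, in both arms and in the same way, any event in the pool, any session stopped early and any withdrawal with its reason. Add these items to the Data Elements to be Abstracted in section 2.0.
2. Extend the sentence in section 2.0 on which pain scores are used, so that the post-minus-pre change in each session is also reported by arm from the readings already taken. Because patients contribute many sessions, summarise the change within each patient first and then by arm. The table is descriptive.
3. Reconcile the risk statement in section 3.0 with the two statements on beats per minute in section 2.0, and those two with each other. How they are resolved is a clinical matter for the investigator.

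The cost is a few flow-sheet fields, a little recording time for the two assistants in the pool and one descriptive table. No new procedure, staff or patients are needed.
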